12.3.6 Other variables

12.3.6.1 TG2 in plasma

At each post-dose timepoint, TG2 levels in plasma will be summarised using descriptive statistics by treatment as absolute value and change from baseline (i.e., the pre-dose assessment on Day 1) using descriptive statistics and 95% CIs.

Time profile plots will be presented by dose level, based on arithmetic means, and by subject, by showing the individual curves grouped by dose level (1 plot for each dose level) and ADA positivity/negativity (using different colours).

The TG2 levels in plasma obtained from healthy subjects will be summarised using descriptive statistics.

Box-plots summarising the pre-dose levels for treated subjects in the study, the healthy subjects' external group, and each post-dose levels for the different doses for treated subjects will be presented.

12.3.7 Interim analysis

Interim analysis not planned.

13. ETHICS COMMITTEE

The study proposal will be submitted to the EC in accordance with the local requirements.

The EC shall give its opinion in writing, clearly identifying the study number, study title and ICF approved, before the clinical study commences.

A copy of all communications with the EC will be provided to the Sponsor.

The Investigator should provide written reports to the EC annually or more frequently if requested on any changes significantly affecting the conduct of the study and/or increasing risk to the subjects (according to the requirements of each country).

14. REGULATORY REQUIREMENTS

The study will be notified to the Health Authorities (or authorised by) according to the legal requirements.

Selection of the subjects will not start before the approval of the EC has been obtained and the study notified to Health Authorities (or authorised by).

Clinical Study Code No.: CLI-10067AA1-01	Version No.: 6.0
EUDRACT No.: 2022-001079-15	Date: 06 July 2023

15. INFORMED CONSENT

Informed consent must be written in a language understandable to the subjects. It is the responsibility of the Investigator to obtain written consent from each subject prior to any study related procedures taking place, by using the latest EC approved version of the document.

Adequate time shall be given to the subject to enquire to the Investigator about any clarification needed and to consider his or her decision to participate to the study.

If the subject is unable to read, the informed consent will be obtained in the presence of an impartial witness, e.g., a person independent of the study who will read and sign the ICF and the written information for the subject.

Consent must be documented by the subject's dated signature. The signature confirms that the consent is based on information that has been understood. Moreover, the Investigator must sign and date the ICF.

Each subject's signed informed consent must be kept on file by the Investigator. One copy must be given to the subject.

For subjects who agree to the collection of optional samples for transcriptomic analysis, separate informed consent must be obtained and the separate optional ICF signed prior to collection.

Female subjects becoming pregnant during the study and partner of a subject participating to the study becoming pregnant will have to sign a specific informed consent form to provide permission to Chiesi to collect information about the pregnancy, its outcome and the birth and health of the newborn child.

16. SOURCE DOCUMENTS/DATA

16.1 Recording of Source Data

Data collection is the responsibility of the clinical study staff at the site under the supervision of the site Investigator. The Investigator is responsible for ensuring the accuracy, completeness, legibility, and timeliness of the data reported. All source documents should be completed in a neat, legible manner to ensure accurate interpretation of data.

Data recorded in the eCRF transcribed from source documents should be consistent with the data recorded on the source documents.

16.2 Direct Access to Source Document/Data

The Investigators or designee must permit study-related monitoring, audits, EC review, or regulatory inspection, providing direct access to source data/documents.

Clinical Study Code No.: CLI-10067AA1-01	Version No.: 6.0
EUDRACT No.: 2022-001079-15	Date: 06 July 2023

17. STUDY MONITORING

Monitoring will be performed by Fortrea who have been designated by Chiesi.

It is understood that the monitor(s) will contact and visit the Investigator/site before the study, regularly throughout the study and after the study had been completed, and that they will be permitted to inspect the various study records: case reports form, Investigator study file, and source data, provided that subject confidentiality is respected.

The purposes of these visits are:

- to assess the progress of the study
- to review the compliance with the study protocol
- to discuss any emergent problem
- to check the eCRFs for accuracy and completeness
- to validate the contents of the eCRFs against the source documents
- to assess the status of drug storage, dispensing, and retrieval.

Prior to each monitoring visit, the Investigator or staff will record all data generated since the last visit on the case report forms. The Investigator and/or study staff will be expected to be available for at least a portion of the monitoring visit to answer questions and to provide any missing information.

It is possible that the Investigator site may be audited by Sponsor personnel or regulatory national and/or international regulatory agencies during and after the study has been completed.

18. QUALITY ASSURANCE

The R&D Quality Assurance Department of Chiesi may perform an audit at any time according to the Sponsor's Standard Operating Procedures, in order to verify whether the study is being conducted in agreement with GCP and the protocol.

19. INSURANCE AND INDEMNITY

Chiesi holds and will maintain an adequate insurance policy covering damages arising out of Chiesi's sponsored clinical research studies.

Chiesi will indemnify the Investigator and hold him/her harmless for claims for damages arising out of the investigation, in excess of those covered by his/her own professional liability insurance, providing that the study treatment was administered under his/her or deputy's supervision and in strict accordance with accepted medical practice and with the study protocol.

The Investigator must notify Chiesi immediately upon notice of any claims or lawsuits.

Clinical Study Code No.: CLI-10067AA1-01	Version No.: 6.0
EUDRACT No.: 2022-001079-15	Date: 06 July 2023

21. PREMATURE TERMINATION OF THE STUDY

Both the Sponsor and the Investigator reserve the right to terminate the study at any time. Should this be necessary, the procedures for an early termination or temporary halt will be arranged after consultation by all involved parties.

The Sponsor should submit a written notification to the Regulatory Authorities concerned and EC providing the justification of premature ending or of the temporary halt.

22. CLINICAL STUDY REPORT

The Clinical Study Report, including the statistical and clinical evaluations, shall be prepared and sent to Coordinating Investigator for agreement and signature.

At the end of the study a summary of the Clinical Study Report will be provided to all EC, to the Competent Authorities and to Investigators.

23. RECORD RETENTION

After completion of the study, all documents and data relating to the study will be kept in an orderly manner by the Investigator in a secure study file.

Regulations require that essential documents must be retained for at least 2 years after the final marketing approval in an ICH region or until 2 years have elapsed since the formal interruption of the clinical development of the product under study.

It is the responsibility of the Sponsor to inform the Investigator of when these documents can be destroyed. The Investigator must contact Chiesi before destroying any study-related documentation. In addition, all subjects' medical records and other source documentation will be kept for the maximum time permitted by the institution.

24. PUBLICATION OF RESULTS

Chiesi is entitled to publish and/or present any results of this study at scientific meetings, and to submit the clinical study data to national and international Regulatory Authorities and, if they

Clinical Study Code No.: CLI-10067AA1-01	Version No.: 6.0
EUDRACT No.: 2022-001079-15	Date: 06 July 2023

fall under the Chiesi commitments on Clinical Trial Transparency, to make them available on www.chiesi.com website.

Chiesi furthermore reserves the right to use such data for industrial purposes.

In the absence of a Study Steering Committee, Investigators will inform Chiesi before using the results of the study for publication or presentation and agree to provide the Sponsor with a copy of the proposed presentation. Data from individual clinical sites must not be published separately.

Clinical Study Code No.: CLI-10067AA1-01	Version No.: 6.0
EUDRACT No.: 2022-001079-15	Date: 06 July 2023

APPENDIX 3 - RECOMMENDATIONS RELATED TO CONTRACEPTION AND PREGNANCY TESTING IN CLINICAL STUDIES

Definition of female of childbearing potential and of fertile men

For the purpose of this document, a woman is considered of childbearing potential (WOCBP), i.e., fertile, following menarche and until becoming post-menopausal unless permanently sterile. Permanent sterilisation methods include hysterectomy, bilateral salpingectomy, and bilateral oophorectomy.

A postmenopausal state is defined as no menses for 12 months without an alternative medical cause. A high follicle-stimulating hormone (FSH) level in the postmenopausal range may be used to confirm a post-menopausal state in women not using hormonal contraception or hormonal replacement therapy. However, in the absence of 12 months of amenorrhea, a single FSH measurement is insufficient.

For the purpose of this document, a man is considered fertile after puberty unless permanently sterile by bilateral orchidectomy.

Birth control methods, which may be considered as highly effective

For the purpose of this guidance, methods that can achieve a failure rate of less than 1% per year when used consistently and correctly are considered as highly effective birth control methods. Such methods include:

- combined (estrogen- and progestogen-containing) hormonal contraception associated with inhibition of ovulation:
 - oral
 - intravaginal
 - transdermal
- progestogen-only hormonal contraception associated with inhibition of ovulation:
 - oral
 - injectable
 - implantable³
- intrauterine device³
- intrauterine hormone-releasing system³
- bilateral tubal occlusion³
- vasectomised partner^{1,3}
- sexual abstinence²

¹ Vasectomised partner is a highly effective birth control method provided that partner is the sole sexual partner of the WOCBP study subject and that the vasectomised partner has received medical assessment of the surgical success.

² Sexual abstinence is considered a highly effective method only if defined as refraining from heterosexual intercourse during the entire period of risk associated with the study treatments. The reliability of sexual abstinence needs to be evaluated in relation to the duration of the clinical study and the preferred and usual lifestyle of the subject.

³ Methods with low-user dependency

Clinical Trial Facilitation Group guidance: Recommendations related to contraception and pregnancy testing in clinical trials. Final version 1.1, 21/09/2020.

ADaM	analysis data model
ADR	adverse drug reaction
AE	adverse event
anti-HBc	hepatitis B core antibody
ATC	anatomical therapeutic chemical
AUC	area under the concentration-time curve
AUC _{0-t}	area under the concentration-time curve, from 0 to the last quantifiable concentration
AUC _{inf}	area under the concentration-time curve, extrapolated to infinity
BLQ	below the limit of quantification
BMI	body mass index
bpm	beats per minute
C _{inf}	concentration at the end of infusion
CI	confidence interval
CL	clearance
C _{max}	maximum observed concentration
eCRF	electronic case report form
CV	coefficient of variation
DBP	diastolic blood pressure
DLCO	diffusing capacity of the lung for carbon monoxide
DRM	data review meeting
DRR	data review report
DY	relative day
ECG	Electrocardiogram
EMA	European Medicines Agency
ENR	enrolled set
FEV ₁	forced expiratory volume in 1 second
FSH	follicle-stimulating hormone
FVC	forced vital capacity

	Statistical Analysis Plan	
CLI-10067AA1-01	Final Analysis	Final 1.0 of 30MAY2024

HBsAG	hepatitis B surface antigen
HIV1	human immunodeficiency virus 1
HIV2	human immunodeficiency virus 2
HR	heart rate
ICF	informed consent form
ICH	International Council for Harmonisation of Technical Requirements for Pharmaceuticals for Human Use
IHR	Immediate Hypersensitivity Reaction
IL	Interleukin
IPF	idiopathic pulmonary fibrosis
IRT	interactive responsive technology
IS	immunogenicity
IV	intravenous
KFR	key first result
mAb	monoclonal antibody
MedDRA	Medical Dictionary for Regulatory Activities
nAb	neutralising antibody
NAP	not applicable
PCR	polymerase chain reaction
PK	pharmacokinetic
QTc	corrected QT interval
QTcF	Fridericia's corrected QT interval
RNA	ribonucleic acid
RND	randomised set
SAF	safety set
SAP	statistical analysis plan
SBP	systolic blood pressure
SD	standard deviation
SDTM	study data tabulation model
SOP	standard operating procedure
STAT	Statistics
$t_{1/2}$	terminal half-life
TEAE	treatment-emergent adverse event
TG2	transglutaminase 2

Statistical Analysis Plan

CLI-10067AA1-01

Final Analysis

Final 1.0 of 30MAY2024

TLF	tables, listings and figures
t_{\max}	time to C_{\max}
t_{\inf}	time to C_{\inf}
TNF- α	tumour necrosis factor- α
UIP	usual interstitial pneumonia
VS	vital signs
V_z	volume of distribution
WBC	white blood cell
WHO	World Health Organisation
WHODrug	WHO drug dictionary

DEFINITION OF TERMS

bias	The systematic tendency of any factors associated with the design, conduct, analysis and evaluation of the results of a clinical trial to make the estimate of a treatment effect deviate from its true value. Bias introduced through deviations in conduct is referred to as 'operational' bias. The other sources of bias listed above are referred to as 'statistical'.
case report form (CRF)	A printed, optical, or electronic document designed to record protocol required information to be reported to the sponsor for each trial subject.
display	Analysis table, listing or figure
missing data	Data that would be meaningful for the analysis of a given endpoint but were not collected. They should be distinguished from data that do not exist.
phase	Interval of time in the planned conduct of a study associated with a specific purpose: for example, screening, treatment, follow-up.
significant digit	All digits of a number used to express it to the required degree of accuracy, starting from the first non-zero digit.
standardised unit	unit populating --STRESU in the clinical database
treatment-emergent abnormality	Any postbaseline abnormality/toxicity that was not present at baseline (e.g., glucose low at baseline and high post-baseline; QTcF]450; 480] ms at baseline and >500 ms post-baseline)

1. INTRODUCTION

This SAP describes the final statistical analysis to be performed for the CLI-10067AA1-01 (████████) study.

This SAP covers the pharmacokinetic (PK), immunogenicity (IS), safety, transglutaminase 2 (TG2) levels, and general characteristics parts of the statistical analysis. It specifies the analysis displays to be presented and describes the methods and procedures in a more elaborated way than in the statistical methods section of the protocol.

The statistical analysis will process and present the results following the International Council for Harmonisation of Technical Requirements for Pharmaceuticals for Human Use (ICH) standards.

1.1 STUDY OBJECTIVES

According to the protocol, the primary objective of this study is:

- to assess the safety and tolerability of single ascending doses of CHF10067 in subjects with IPF.

According to the protocol, the secondary objectives of this study are:

- to evaluate the CHF10067 PK profile in serum;
- to evaluate the CHF10067 immunogenicity profile in terms of anti-drug antibody (ADA) and neutralising antibody (nAb).

According to the protocol, the exploratory objective of this study is:

- to evaluate TG2 levels in plasma.

1.2 STUDY DESIGN

[figure not shown]
This is a Phase Ib, multi-centre, multi-country, randomised, double-blind, placebo-controlled study to investigate the safety, tolerability, immunogenicity, and PK of single IV doses of CHF10067 in subjects with IPF. The effect of CHF10067 on TG2 levels will also be investigated as an exploratory endpoint.

Overall, 24 subjects will be enrolled in 3 cohorts (Cohorts A [1000 mg], B [anticipated 2000 mg], and C [anticipated 3000 mg]) consisting of 8 subjects per cohort. In each cohort, 6 subjects will receive CHF10067, and 2 subjects will receive placebo.

The doses will be administered according to an escalation scheme designed to ensure sufficient safety conditions for subjects. In each cohort, subjects will be divided into 2 sub-groups, with each sub-group being dosed at least 24 hours apart. The first sub-group will comprise 2 subjects, with 1 subject receiving CHF10067 and 1 subject receiving placebo. The second sub-group will comprise 6 subjects, with 5 subjects receiving CHF10067 and 1 subject receiving placebo. Continuation to dose the remaining 6 subjects will be evaluated by at least the Medical Monitor and Sponsor Clinical Research Physician based on the safety data provided by the Investigator(s) where the first-sub-group have been dosed. The decision to escalate to the next dose will be made by the Safety Advisory Committee when safety data until Day 14 have been collected for all subjects at the previous dose level. Pharmacokinetic and

immunogenicity data will also be included in the safety evaluation for dose escalation (if available) but are not mandatory to escalate to the next dose.

An overview of the study design is shown in the figure below.

The schedule of assessments is in appendix 10.1.

1.3 EXPECTED SAMPLE SIZE

This study is designed to explore the safety and tolerability of CHF10067 for the first time in subjects affected by IPF, while exposing a minimum number of subjects; therefore, no formal power calculation was performed.

A sample size of 24 subjects (8 subjects per cohort; 6 treated with CHF10067 and 2 with placebo) is deemed adequate to assess safety and tolerability of CHF10067. In each cohort, a minimum of 2 subjects are required to be not receiving antifibrotic treatment (including subjects with previous use of antifibrotic treatment that has been stopped for at least 2 weeks prior to screening).

1.4 RANDOMISATION AND BLINDING

An interactive responsive technology (IRT) system will be used for randomisation and assignment to blind treatment (CHF10067 or placebo).

The Investigator, or designee, at the sites will use the IRT system to screen and randomise subjects and to assign treatment kits according to the randomisation list. Subjects will be randomised in a 3:1 ratio within each cohort to receive either CHF10067 or placebo. Randomisation will require a minimum of 2 subjects within each cohort not receiving antifibrotic treatment (including subjects with previous use of antifibrotic treatment that has been stopped for at least 2 weeks prior to screening). In each cohort, at least 24 hours must elapse between dosing of the first 2 subjects (1 CHF10067; 1 placebo) and the remaining 6 subjects. The IRT system will be used to coordinate the scheduling of Day 1 visits to be sure that this procedure is followed.

1.5 INTERIM ANALYSIS

No interim analyses are foreseen.

1.6 SOFTWARE

SAS version 9.4 (SAS Institute Inc., Cary, NC, USA) will be used for programming.

Statistical Analysis Plan

CLI-10067AA1-01

Final Analysis

Final 1.0 of 30MAY2024

Phoenix WinNonlin 8.3 or later (Certara, NJ, USA) will be used for calculations of PK parameters.

1.7 VALIDATION MODEL

SGS Statistics (STAT) and Pharmacokinetics (PK) standard operating procedures (SOPs) and work instructions (WIs) as effective at the time of the activity will be followed throughout the project, provided the applicable regulatory requirements are still met.

The analysis tables/figures/listings will be reviewed by an independent person (validated according to model B; see SOP.STAT.020 and SOP.PK.020).

PK analysis will be validated according SOP.PK.001.

2. PHARMACOKINETIC, AND IMMUNOGENICITY ANALYSES

2.1 PHARMACOKINETIC ANALYSES

2.1.1 Available data

Blood samples will be collected for the determination of CHF10067 in serum at the following time points: pre-dose (within 75 minutes from start of infusion), at the end of infusion, and 2, 4, 8, and 20 hours after the end of the infusion and 5, 7, 14, 28, 56 and 84 days post-dose.

2.1.2 Endpoints and derivation rules

The following PK parameters will be derived for serum CHF10067:

- AUC_{0-t} , AUC_{inf} , C_{max} , t_{max} , C_{inf} , t_{inf} , CL , V_z , $t_{1/2}$.

Standard non-compartmental methods will be used for the calculation of the PK parameters from the individual serum concentration – time profiles using actual sampling time points from start of infusion. If actual sampling time is not available, nominal time will be used (see also section 6.1.3.1). The analysis will consider time only in hours and minutes. Any seconds in the time part of a record will be imputed by zero. The area under the serum concentration-time curve (AUC) will be calculated according to the linear trapezoidal method.

PK parameters definition

- AUC_{0-t} : AUC from 0 to the last quantifiable concentration;
- AUC_{inf} : AUC from 0 to infinite time calculated as: AUC extrapolated to infinity will be calculated as the sum of AUC_{0-t} and a residual part extrapolated to infinite time. The residual area from the last concentration data point to infinite time is calculated using the approximation:

$$\int_t^{\infty} C_t dt = C_t / \lambda_z$$

where λ_z is the first order terminal rate constant, estimated by linear regression of the terminal loglinear segment of the plasma log concentration curve, and C_t is the last quantifiable concentration data point;

- C_{max} and t_{max} : the value and time of the maximum serum concentration will be obtained directly from the experimental data without interpolation;
- C_{inf} and t_{inf} : the value and time of the serum concentration at end of infusion;
- CL : clearance will be calculated as:

$$Dose / AUC_{inf}$$

- V_z : volume of distribution will be calculated as:

$$Dose / (\lambda_z * AUC_{inf})$$

	Statistical Analysis Plan	
CLI-10067AA1-01	Final Analysis	Final 1.0 of 30MAY2024

- $t_{1/2}$: terminal half-life, associated with negative slope ($-\lambda z$), will be calculated as $0.693/\lambda z$ from the individual drug concentration time profiles

Criteria for $t_{1/2}$ estimation

- At least three time points (excluding t_{max}) should be used for the determination of the elimination rate constant (λz), otherwise the $t_{1/2}$ as well as the derived parameters (AUC_{inf} , CL and Vz) cannot be estimated and will be presented as “NE” (not estimated) in the tables.
- The adjusted correlation coefficient of the linear regression should be ≥ 0.85 , otherwise the $t_{1/2}$ as well as the derived parameters (AUC_{inf} , CL and Vz) are not reliably estimated and will not be reported (presented as “NR” (not reported) in the tables).

Criteria for AUC_{inf} estimation

- When for a profile the $AUC_{extrapolated} / AUC_{0-\infty} > 20\%$, this AUC_{inf} as well as the derived parameters (CL and Vz) will be excluded from the statistical analyses.

All PK parameters will be estimated, if feasible, and presented in the TLFs, unless specified differently (e.g., unreliable $t_{1/2}$). PK parameters that cannot be estimated will be specified in the Data Review Report (DRR) (*prior* to database lock and disclosure of the bioanalytical data) and/or PK DRR (*after* database lock and disclosure of the bioanalytical data). PK data that is excluded from PK analysis will be discussed in the DRR and/or PK DRR, and marked in the relevant tables, accompanied with a footnote.

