7.2.1.2 Determination of CHF10067

Blood samples (1 sample = 3.5 mL) for determination of serum CHF10067 will be collected at the following timepoints: pre-dose (within 75 minutes from start of infusion), at the end of infusion, 2, 4, 8, and 20 hours after the end of infusion and 5, 7, 14, 28, 56, and 84 days post-dose. The selected timepoints are based on the results obtained after single dose in healthy subjects. Timepoints may be adjusted during the study if the PK profile in IPF patients is significantly different than healthy subjects. In that case, decisions will be taken by the Safety Advisory Committee and appropriately documented. The total number of timepoints is not expected to be modified.

The time deviation window for PK sampling will be:

- \pm 5 minutes for timepoints \leq 2 hours
- \pm 15 minutes for timepoints $>$ 2 hours and \leq 8 hours
- \pm 1 hour for the timepoint of 20 hours
- \pm 1 day for Days 5 and 7
- \pm 2 days for Days 14, 28, 56, and 84.

The processing, storage and shipment of samples are detailed in the Laboratory Manual document.

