For serum PK assessments not performed or not reportable at the last planned sampling time point, the following schema will be used to determine the handling of impacted AUCs (C_x , C_y and C_z are adjacent concentration samples at the end of the profile, with $t_x < t_y < t_z$; thus t_z being the last planned sampling time point of the profile):

Multiple missing PK assessments

The impact of multiple PK assessments not performed or not reportable, i.e., at least 2 adjacent intermediate values are missing, or more than 3 intermediate values are missing, the PK profiles will be discussed case by case in the DRR and/or PK DRR. If 1, or 2 non adjacent intermediate values are missing, no impact on PK parameter estimation is expected.

Two serum samples at the same actual time

The Phoenix WNL software cannot handle two identical actual sampling time points in a profile. Therefore, if two serum samples are taken at the same time, the sample taken closest to the planned sampling time point will be used while the other will be excluded from PK parameter estimation.

Rules after disclosure of the bioanalytical data

After disclosure of the bioanalytical data, subjects and/or PK data will not be excluded based on post-hoc statistical analysis or for pharmacokinetic reasons, except for certain cases described below (in line with the EMA guideline on the investigation of bioequivalence CPMP/EWP/QWP/1401/98 Rev.1 2010).

All BLQ values

When plasma concentrations are BLQ at all time points, no PK parameters will be estimated and the subject will be excluded from the PK set.

Non-zero baseline concentration > 5% of C_{max}

Statistical Analysis Plan

CLI-10067AA1-01

Final Analysis

Final 1.0 of 30MAY2024

Subjects with Day 1 pre-dose values exceeding 5% of the C_{max} will be excluded from the PK set.

AUC_{0-t} lower than 5% of the corresponding geometric mean AUC_{0-t}

Subjects with an AUC_{0-t} lower than 5% of the corresponding geometric mean AUC_{0-t} (calculated without inclusion of data from the outlying subject) will be excluded from the PK set.

Abnormal PK concentrations or profiles

Abnormal PK concentrations or profiles will be discussed case by case in the PK DRR.

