Next to the screening value, all assessments, including unscheduled assessments, will be allocated to analysis windows. Tables will present the analysis windows as defined below and listings will present the analysis windows, as well as the eCRF visits. Allocation of assessments will be done according to the following tables:

Pharmacokinetics:

Analysis time point window	Target time after end of infusion (hours)	Time interval (hours)
Pre-dose	<0	Last day 1, pre-dose assessment
EOI	0	[0 min; 10 min=0.1667]
2h	2	[11 min=0.1833; 3]
4h	4	[3.0167; 6]
8h	8	[6.0167; 14]
20h	20	[14.0167; 58]
Day 5	96	[58.0167; 120]
Day 7	144	[120.0167; 228]
Day 14	312	[228.0167; 480]

Statistical Analysis Plan

CLI-10067AA1-01

Final Analysis

Final 1.0 of 30MAY2024

Day 28	648	[480.0167;984]
Day 56	1320	[984.0167;1656]
Day 84	1992	[1656.0167;∞)

Vital signs and oxygen saturation:

Before and during infusion:

Analysis time point window	Target time vs. start of infusion (minutes)	Time interval (minutes)
Pre-dose	<0	Last day 1, pre-dose assessment
0.25h	15	[1;22]
0.5h	30	[23;37]
0.75h	45	[38;52]
1h	60	[53;67]
1.25h	75	[68;82]
1.5h	90	[83;97]
1.75h	105	[98;112]
2h	120	[113;127]
2.25h	135	[128;142]
2.5h	150	[143;157]
2.75h	165	[158;172]
3h	180	[173;187]
3.25h	195	[188;202]
3.5h	210	[203;217]
3.75h	225	[218;232]
4h	240	[233;247]
4.25h	255	[248;262]
4.5h	270	[263;277]
4.75h	285	[278;292]

Statistical Analysis Plan

CLI-10067AA1-01

Final Analysis

Final 1.0 of 30MAY2024

5h	300	[293; 307]
5.25h	315	[308; 322]
5.5h	330	[323; end of infusion]

After infusion:

Analysis time point window	Target time vs. end of infusion (minutes)	Time interval (minutes)
0h	0	[End of infusion; 5]
0.5h	30	[6;45]
1h	60	[46;90]
2h	120	[91;150]
3h	180	[151;210]
4h	240	[211;300]
6h	360	[301;420]
8h	480	[421;840]
20h	1200	[841;1560)

Systemic markers:

Analysis time point window	Target time vs. end of infusion (pre-dose) or start of hypersensitivity reaction (post-dose) (minutes)	Time interval (minutes)
Pre-dose	<0	Last day 1, pre-dose assessment
1h	60	[1;90]
2h	120	[91;∞)

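### SAP 2.1.2 uses the linear trapezoidal rule across late sampling gaps of 14 and 28 days; under log-linear decline with an assumed half-life of 14 to 28 days, AUCinf reads about 5 to 2% high and CL and Vz about 5 to 2% low

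*SAP*

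**What the plan says.** SAP 2.1.2 fixes one AUC rule for the whole profile: "The area under the serum concentration-time curve (AUC) will be calculated according to the linear trapezoidal method". Protocol 8.1 asks only for standard non-compartmental methods and names no trapezoidal rule, so the SAP alone sets it.

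SAP 2.1.1 places the later samples at "20 hours after the end of the infusion and 5, 7, 14, 28, 56 and 84 days post-dose". The last three gaps are therefore 14 days (Day 14 to 28), 28 days (Day 28 to 56) and 28 days (Day 56 to 84). On the choice of times, Protocol 7.2.1.2 says: "The selected timepoints are based on the results obtained after single dose in healthy subjects".

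In SAP 2.1.2, lambda-z is "estimated by linear regression of the terminal loglinear segment of the plasma log concentration curve". At least three time points, not counting tmax, "should be used for the determination of the elimination rate constant". AUCinf is AUC0-t plus Ct/lambda-z, CL is Dose/AUCinf, and Vz is Dose/(lambda-z × AUCinf). If more than 20% of AUCinf is extrapolated, that AUCinf "as well as the derived parameters (CL and Vz) will be excluded from the statistical analyses". Under SAP 6.1.3.1, a subject whose AUC0-t is "lower than 5% of the corresponding geometric mean" leaves the PK set.

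**The concern.** Over a long gap in a log-linear decline, the straight line between two samples overstates the area. The error has the same sign in every subject, so more subjects would not average it out. It passes inversely into CL and Vz.

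The last three scheduled samples are Days 28, 56 and 84. When all are quantifiable, every lambda-z fit includes them. The same two 28-day gaps are then log-linear for lambda-z and straight for AUC0-t, and AUCinf and Vz combine the two.

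The PK profile is a secondary objective. Protocol 1.2 says that the PK data will help to choose doses for later studies, so the absolute AUC and CL values may be reused. No planned table or figure shows how much of them comes from the integration rule.

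**Working it through.** The plan states no figure to reproduce, so this is a direct calculation.

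**Inputs from the documents.** Target times after end of infusion (SAP 6.2.4, PK window table): 0, 2, 4, 8, 20, 96, 144, 312, 648, 1320 and 1992 h. AUCinf, CL, Vz and the 20% rule are as in SAP 2.1.2.

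**Assumptions.** Half-life 7 to 28 days (none is given); mono-exponential decline; all samples quantifiable; 2 h infusion (the duration is not public; 1 h or 5.5 h changes results by at most 0.1 point).

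**Formula.** For a gap of length g and rate constant k, put x = k·g. The linear rule overstates the area of that gap by the fraction (x/2)·coth(x/2) − 1. The effect on AUCinf is this fraction times the gap's share of the true AUCinf.

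**Example, half-life 14 days** (shares as after a short infusion; the gaps start 13, 27 and 55 days after end of infusion and the last ends at 83):
- Day 14–28: x = 0.693, excess 3.97%; share 2^(−13/14) − 2^(−27/14) = 0.263; contribution 1.04 points.
- Day 28–56: x = 1.386, excess 15.5%; share 2^(−27/14) − 2^(−55/14) = 0.197; contribution 3.05 points.
- Day 56–84: excess 15.5%; share 2^(−55/14) − 2^(−83/14) = 0.049; contribution 0.76 points.
- These three gaps give 4.9 of the total 5.1 points. CL and Vz: 1/1.0511 − 1 = −4.9%.

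| Assumed half-life | AUCinf | CL and Vz | Points from the three late gaps |
|---|---|---|---|
| 7 d | +8.4% | −7.8% | 7.1 |
| 10 d | +7.0% | −6.5% | 6.4 |
| 14 d | +5.1% | −4.9% | 4.9 |
| 21 d | +2.9% | −2.8% | 2.8 |
| 28 d | +1.8% | −1.7% | 1.7 |

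On the same samples the linear-up/log-down error is below 0.01%. Cmax, Cinf and t1/2 do not depend on the rule.

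**Limits of the range.** The extrapolated share reaches 20% at a half-life of about 36 days, where the AUCinf error is 1.1%; beyond that, AUCinf, CL and Vz are excluded. At 7 days, Day 84 is about 12 half-lives out, with a level of 0.03% of that at end of infusion.

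**Sensitivity.** Reading Day d as d days after dosing gives +4.9% at 14 days and +1.7% at 28 days. A bi-exponential decline (assumed early half-life 1 to 2 days, weight 0.4 to 0.6) gives +5.9 to +6.5% at 14 days and +2.3 to +2.8% at 28 days.

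**Power-model slope.** The shift is Σ(ln d − mean)·ln(1 + error) / Σ(ln d − mean)². For 1000, 2000 and 3000 mg the deviations are −0.597, 0.096 and 0.501, with sum of squares 0.617.
- Same half-life at all doses: 0.
- 14/21/28 days: −0.029.
- 7/14/21 days: −0.047.
- 7/14/28 days: (−0.597 × 0.0810 + 0.096 × 0.0498 + 0.501 × 0.0176)/0.617 = −0.056.

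With 6 subjects per dose, the 90% CI half-width of the slope is 0.18, 0.27 or 0.35 at an assumed CV of 20, 30 or 40%.

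**Sampling error of a 6-subject geometric mean, assumed CV 30%.** The log-scale SD is √ln(1.09) = 0.294, so the 90% CI is exp(±2.015 × 0.294/√6) − 1, or about −21% to +27%.

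**Accelerating elimination.** I took 36 illustrative profiles: half-life 14, 21 or 28 days, shortening to 2, 4 or 7 days at Day 20, 30, 40 or 50, with an assumed quantification limit of 0.1% of Cmax. For AUC0-t the linear error ran from −5.7 to +13.3% and the log-down error from 0 to −15.8%. Log-down was closer in 15, and both methods read low in 9. In 31 profiles AUCinf also meets the SAP's reporting criteria. There log-down was closer in 16, with mean absolute AUCinf error 5.5% against 4.9% for linear.

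**The case against.** The strongest reply is that the sponsor chose a rule openly and in advance, and nothing in either document contradicts it. That stands. A reader might infer that a log-linear lambda-z beside a linear AUC is an inconsistency in the plan. It is not: SAP 2.1.2 defines the two separately, and the point is about accuracy.

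The second reply is that nothing turns on it. This largely stands too. AUC, CL and Vz are summarised descriptively, PK data are not mandatory for escalation, and AUC and CL for ADA-positive subjects appear only in a listing. The error is small beside the sampling error of six subjects, although unlike that error it is systematic. The difference can also be recovered, because individual concentrations and actual times are tabulated and the individual log-linear plots show the shape of the decline. But the reader would have to do that work, and the reported AUC, CL and Vz would still carry the error.

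The third reply is that log-down is not uniformly better. In the 36 accelerating profiles the mean absolute AUC0-t error was 4.2% for linear and 6.1% for log-down, and the plan does look for ADA effects on PK. For AUCinf, CL and Vz, which need an acceptable terminal log-linear fit, the two methods come out about even in those profiles. Under log-linear decline, log-down is clearly better.

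**Conclusion.** The point holds at the low end of minor. If the decline is roughly mono-exponential and the half-life is 14 to 28 days, AUCinf reads about 5 to 2% high and CL and Vz about 5 to 2% low. Both conditions are assumptions.

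Three stronger readings are not supported:
- **An error of about 8%.** That needs a half-life near 7 days. The times were chosen from healthy-subject results, so sampling to Day 84 suggests a longer one, though it does not prove it.
- **A dose-proportionality result at risk, or a slope shift that can never exceed 0.06.** The shift is zero with a common half-life and at most about 0.06 in the mono-exponential 7 to 28 day examples. That bound does not cover accelerating elimination. Setting the extreme AUC0-t errors above at the highest and lowest dose gives ln(1.133/0.943)/ln 3, about 0.17, but that pairing is contrived.
- **Two methods that bracket the truth.** With accelerating elimination both can read low.

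**What to change.** Before bioanalytical data are disclosed, replace the AUC sentence in SAP 2.1.2 with text such as:

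> AUC0-t, AUCinf, CL and Vz will be calculated by the linear-up/log-down trapezoidal method. This is the primary set and is the only one used for the power model, the 20% extrapolation rule and the 5% AUC0-t exclusion rule. Values by the linear trapezoidal method will be tabulated alongside for comparability with earlier studies.

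Naming one primary set keeps a single PK set and one slope per parameter. If the data have already been disclosed, the second set can still be reported, labelled post hoc.

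The cost is one or two SAP sentences, one Phoenix WinNonlin setting and one extra table next to Table 14.2.2.3. No protocol amendment is needed, because Protocol 8.1 names no trapezoidal rule. The downside is a second set of values to explain, and a primary method that reads low if elimination accelerates, for example through saturable or ADA-related clearance. The individual log-linear plots already planned should be read for that shape before either set is relied on.
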